16.1.3 Randomization and Factors for Stratification

Participants will be randomized in a 1:1 ratio to BUP-Inj or PBO-Inj, using a permuted block design with random block sizes and stratified by enrolling site. A separate randomization plan will be developed with additional details regarding treatment allocation. Given that the study is double-blind, only certain staff at the DSC and CCC will be able to access individual treatment assignments and detailed information contained in a separate Blinding Management Plan.

16.2 Rationale for Sample Size and Statistical Power

A sample size of 246 was chosen for this study to provide 90% power to detect a statistically significant difference between the two treatments. Power was based on an effect size derived from the proportion of MA-negative urines during the last 4 weeks of Phase I of the ADAPT-2 study (CTN-0068) comparing the active treatment arm to the placebo arm. Imputing all missing data as positive, the relevant proportions in ADAPT-2 were 0.17 and 0.07 in the treated (AMC) and control (PBO) arms respectively, so we take the treatment effect of interest for MURB to be a risk difference of 0.10 corresponding to an odds ratio of 2.72. This outcome from the ADAPT-2 study was chosen because it was believed to be the most comparable available result using this substance-using population to the BUP-Inj outcome for this study.

To simulate data for CTN-0110, we first imputed all missing ADAPT-2 visits as UDS-positive for MA, then bootstrapped the ADAPT-2 participants, keeping the participant's site and visits together, thus respecting whatever temporal and site-dependent correlations might exist in the data. We assumed equal treatment allocation. To draw bootstrap samples of size N, we bootstrapped differently under null and alternative hypotheses as follows:

- Null: We treated the two simulated treatments the same way: for each of the N/2 simulated participants receiving that treatment, we flipped a fair coin to decide which ADAPT-2 arm (109 AMC and 294 PBO) to draw it from, and then drew it randomly with replacement from that arm.

- Alternative: For AMC, we drew $N/2$ observations randomly with replacement from the 109 AMC patients. For PBO, we drew $N/2$ observations randomly with replacement from the 294 PBO patients.

[figure not shown]
To simulate 2 UDS per week we used all 8 visits of a participant in order. The model under which we performed the power analysis is the same as that to be used for the primary analysis, discussed in Section 16.3.

Simulated power for the generalized estimating equation⁶⁹ is shown as a function of total N ($N/2$ in each arm) in Table 16.1 and in Figure 16.1, in which the total sample size required for power (0.8, 0.9) is interpolated from the simulated data using a logistic function, and estimated to be (182, 246).

Table 16.1: Simulated power for the GEE as a function of total N ($N/2$ in each arm)

Total N	Power
100	0.55
150	0.74
200	0.84
250	0.91
300	0.96
350	0.97

Figure 16.1: Logistic function fitted to simulated power for the GEE as a function of total N ($N/2$ in each arm)

16.2.1 Projected Number of Sites

A total of 4-8 sites will participate in the trial.

16.2.2 Projected Number of Participants per Site

It is anticipated that each site will randomize approximately 31-61 participants over the recruitment period. The enrollment for all sites will be competitive.

16.3 Statistical Methods for Primary and Secondary Outcomes

16.3.1 Primary Outcome

UDS will be collected twice a week during Weeks 9 through 12, or 8 assessments. For each assessment, the outcome will be 1 if the UDS is MA negative and 0 if the UDS is MA positive or missing. The probability of an MA negative UDS during Weeks 9-12 will be computed via a GEE approach postulating a binomial distribution with a logit link, an AR(1) correlation for the repeated observations of a single participant, and utilizing the robust (sandwich) estimator for the covariance of the regression betas. Despite other possible sources of variance such as random site effects, the regression coefficients will be asymptotically unbiased with consistent standard errors using this estimation strategy. The model will have a term for treatment group (BUP-Inj and PBO-Inj) as the between-subjects factor. The model will be used to compute an average probability of MA-negative UDS across Weeks 9 through 12 in each group. Letting y_{it} be an indicator of whether the UDS for participant i ($i=1, \dots, n$) at timepoint t during this evaluation period ($t=1, \dots, 8$), and z_i is an indicator of participant i being assigned to the BUP-Inj arm, the logistic model is given by

$$\text{logit } P(y_{it} = 1) = \alpha + \beta z_i.$$

The hypothesis will be tested by the statistical significance of the odds ratio using a two-sided test (i.e., $H_0: e^\beta = 1$; $H_1: e^\beta \neq 1$). An *a priori* alpha (i.e., type I error) of 0.05 will be used for this analysis.

SAS code to estimate the primary outcome follows:

```
proc genmod data = dat;
  class patid treat;
  model metneg(event = "1") = treat / dist = bin link = logit;
  repeated subject = patid / type = ar(1);
  run;
```

Where `patid` is the participant's unique identifier, `treat` is an indicator of being assigned to the BUP-Inj treatment arm, and `metneg` is an indicator of whether the UDS is negative for MA.

16.3.2 Secondary Outcomes (medication phase, Weeks 1-12):

1. *Alternate measures of methamphetamine use: both*

- a. MA Treatment Effectiveness Score (TES), as measured by number of UDS results negative for MA by condition, during Weeks 1-12 (score range 0-24) will be analyzed as count data, which typically follows a Poisson distribution.

However, we expect there will be more subjects with 24 negative UDS than would be expected based on the Poisson distribution (ceiling effect). Also, there may be more subjects with 0 negative UDS than determined by the Poisson distribution (floor effect). Given the presence of ceiling and floor effects a more flexible model is needed than the hurdle model or zero-inflated Poisson model that would typically be used with count data with floor effects. Therefore, a beta-binomial regression model is anticipated⁷⁰. In this approach, the number of negative UDS is modeled as the number of 'successes' in 24 trials where each trial can result in a success or failure (UDS negative or positive) outcome. The probability of success across subjects is modeled with the beta distribution which is flexible enough to allow for a 'U' shaped distribution with both ceiling and floor effects or only ceiling effects depending on which parameters of the beta distribution are selected. The model will have terms for time, treatment group, treatment group by time interaction, baseline measure of the outcome, and any covariates. The primary hypothesis will be tested by significance of the main effect or interaction effect⁷¹.

- b. Self-reported days of MA use during Weeks 1-12 (score range 0-84) will be analyzed using TLFB data that will be collected in Weeks 1-12 with days of use counted over that period. Count data typically follow a Poisson or Negative Binomial distribution. However, we expect that there will be more participants with zero positive UDS than expected under these distributions (floor effect). We do not expect ceiling effects for this outcome. We will deal with the excess zeros using a hurdle model in which it is assumed that all participants have the potential to use drugs but "resistance" to drug use, or a hurdle, must be overcome before drugs are used. The existence of the hurdle results in an excess of participants with zero positive UDS⁷². The hurdle model will contain a random participant effect, treatment group (buprenorphine vs control), baseline number of use days (in the 30 days before written consent) and any other covariates needed to improve balance between the intervention and control groups. If the data are not zero-inflated, Poisson regression will be used.

2. *Measures of opioid use:* both

- a. Opioid Treatment Effectiveness Score (TES), as measured by number UDS results negative for opioids by condition, during Weeks 1-12. Results from radio-immune assay strips will be used to measure opiates (OPI-300), oxycodone / synthetic opioids, fentanyl for each UDS and
- b. Self-reported frequency of opioid use during Weeks 1-12. Reports of any opioid used will be combined into one measure that includes opiates, oxycodone and synthetic opioids, fentanyl and analogues for each report, will be analyzed using a hurdle model (ceiling effects are not expected) similarly as described for the secondary outcome 1b.

3. Measures of MA and opioid co-use: both

- a. MA and Opioid Treatment Effectiveness Score (TES), as measured by number of same-day UDS results negative for MA and opioids by condition, during Weeks 1-12 and
- b. Self-reported days of both MA and opioid use during Weeks 1-12. All data related to opioid use will be compiled as detailed in secondary outcome 2 and will be analyzed using a hurdle model (ceiling effects are not expected) similarly as described for the secondary outcome 1b.

[figure not shown]

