7.0 OUTCOME MEASURES

7.1 Primary Outcome Measure

The primary outcome measure is the number of MA-negative UDS results obtained during Weeks 9 through 12 of the medication phase as measured for the BUP-Inj and PBO-Inj conditions.

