16.4 Significance Testing

The primary outcome will be evaluated using a two-sided test with a type I error rate of 5%. There are numerous secondary outcomes; however, multiple comparisons will not be adjusted for since these are not part of the study's primary objective.

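### The primary AR(1) GEE with a treatment-only mean weights the eight urines unequally, so it does not estimate the equal-weight count that defines the outcome; the null test stays valid and the fix is cheap

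*Combined protocol and SAP*

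**What the plan says.** Section 7.1, repeated in Section 16.1.2, makes the outcome a count: "The primary outcome measure is the number of MA-negative UDS results obtained during Weeks 9 through 12 of the medication phase". Section 16.3.1 sets the number of records, "UDS will be collected twice a week during Weeks 9 through 12, or 8 assessments", and the missing-data rule: "For each assessment, the outcome will be 1 if the UDS is MA negative and 0 if the UDS is MA positive or missing".

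The model is a logistic GEE with "an AR(1) correlation for the repeated observations of a single participant, and utilizing the robust (sandwich) estimator". On the mean structure: "The model will have a term for treatment group (BUP-Inj and PBO-Inj) as the between-subjects factor". There is no time term. The SAS code agrees: treatment is the only regressor, and the correlation is set in the line beginning "repeated subject = patid / type = ar(1". The synopsis (Section 2.1, Analyses) names the same working correlation.

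The reported quantity is described so: "The model will be used to compute an average probability of MA-negative UDS across Weeks 9 through 12 in each group". Section 16.3.1 also calls the coefficients asymptotically unbiased. Section 16.2 says the power simulation used this same model. No section gives a value for the within-participant correlation or says how visits are weighted.

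**The concern.** A count out of eight gives every urine the same weight. A GEE with a non-trivial working correlation and no time term need not, because the working correlation fixes how the visits are combined. If the combination is unequal, two participants with the same number of negative urines contribute differently. Two trials with the same mean counts per arm can then report different odds ratios. The weights would also depend on a correlation estimated from the final data, so the quantity being estimated is not fully fixed in advance.

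The visits that gain weight are not ordinary ones. The third injection is due at the start of Week 9 (Section 10.4.2), so the first urine falls at about that time. The second Week 12 visit carries several end-of-medication items (Table 11.1). A missed urine scores as positive, so any unusual attendance at these two visits would enter with extra weight.

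**Working it through.** **1. The plan's own figures.** (0.17/0.83)/(0.07/0.93) = 2.72, as Section 16.2 states. A logistic curve refitted to the six rounded points of Table 16.1 (binomial fit) gives N = 181 for 80% and 239 for 90% power, against 182 and 246, with power 0.908 at 246. The bootstrap cannot be rerun without the earlier trial's participant data.

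**2. The weights.** All participants have eight records and the modelled mean is constant within an arm. The arm estimate is therefore a weighted mean of the eight visit proportions, with weights proportional to the row sums of the inverse working correlation. For AR(1) these are 1/(1 + rho) for the first and last visits and (1 - rho)/(1 + rho) for the six between. The share of the two end urines is

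2/(2 + 6(1 - rho)) = 2/(8 - 6 rho).

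| rho | 0 | 0.3 | 0.5 | 0.7 | 0.9 |
|---|---|---|---|---|---|
| share of two end urines | 25% | 32% | 40% | 53% | 77% |

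On one simulated data set (estimated rho 0.556), the closed form and a fitted AR(1) GEE both gave log OR 1.644. Independence and exchangeable fits both gave 1.738.

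**3. A plausible rho.** This is an inference from Table 16.1, not a figure in the protocol. It assumes a Wald test on the logit scale and the same correlation in both arms. Take the row N = 250 (125 per arm), power 0.91:

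- Implied SE = ln(2.72)/(1.960 + 1.341) = 1.001/3.301 = 0.303; variance 0.0920.
- Variance with one urine each = [1/(0.17 x 0.83) + 1/(0.07 x 0.93)]/125 = 22.448/125 = 0.1796.
- Ratio = 0.0920/0.1796 = 0.512.
- If the data are AR(1): (1 + rho)/(8 - 6 rho) = 0.512, so rho = 0.760 and the share is 58%. Each end urine weighs 0.29 and each interior urine 0.07.
- If the data are exchangeable but weighted as AR(1): rho + (1 - rho) x (sum of squared weights) = 0.512, so rho = 0.436 and the share is 37%. The weights are 0.19 and 0.10.

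The other rows and the stated 182 and 246 give shares of 36-38% and 56-60%.

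**4. When the expected estimate moves.** The weights are symmetric about the middle of the window. A constant or linear course in the MA-negative rate therefore gives the same expectation as equal weights: risk difference 0.100, OR 2.72. Only a contrast between ends and middle matters. Assumed examples, each with a BUP-Inj equal-weight mean of 17% and placebo flat at 7%:

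| BUP-Inj ends / middle | rho 0.436 | rho 0.760 |
|---|---|---|
| 21% / 15.7% | RD 0.106, OR 2.85 | RD 0.118, OR 3.07 |
| 13% / 18.3% | RD 0.094, OR 2.60 | RD 0.082, OR 2.39 |

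For the top right cell: 0.5814 x 0.21 + 0.4186 x 0.1567 = 0.1877; minus 0.07 gives 0.118.

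Now let the same visit effect act in both arms, with the visit-specific OR held at 2.72. The OR is 2.71 under either weighting. The RD becomes 0.103-0.109 (higher ends) or 0.096-0.090 (lower ends).

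**5. Power under equal weights, N = 246.** If the data are exactly AR(1) with rho 0.760, the variance factor of the equal-weight mean is 0.551 against 0.512. The SE rises by the square root of 0.551/0.512, about 3.7%, and power falls from 90.6% to 88.4%. If the data are exchangeable with rho 0.436, the factor is 0.507 and power rises to 90.9%. In simulations of 3,000 trials each, AR(1) against independence gave 0.916/0.910, 0.931/0.930 and 0.885/0.893.

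**The case against.** The best defence is that AR(1) with a robust standard error is prespecified consistently in the synopsis, Section 16.3.1 and the code, and was used for the power simulation. Under the stated mean model the MA-negative probability is constant across the window. If so, every weighting has the same expectation, and the claim of asymptotic unbiasedness is correct. Both arms share the weights, so the comparison is like with like. Null simulations rejected at nearly the same rate under AR(1) and equal weights (5.0% against 5.2%; 6.1% against 6.1%). If the true correlation is strongly autoregressive, AR(1) is the more powerful choice.

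All of that stands, and it rules out several stronger readings that a reader might infer:

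- *That the primary test is invalid or the estimate biased.* The test is valid when there is no effect at any visit, and the expected estimate moves only under a particular time course that no section documents.
- *That a 37-58% share is a property of the plan.* It rests on a rho inferred from rounded power values under two assumed structures.
- *That unusual attendance at the Week 9 injection and Week 12 exit visits would distort the odds ratio.* Both arms follow one schedule (Section 6.1.2, Table 11.1), and a shared effect leaves the OR at 2.71. An arm-specific effect is needed, and the protocol gives no evidence of one. Many Week 12 items are also preferred at the first visit of that week.

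The defence does not remove the mismatch itself. The outcome is a count, and the fitted quantity is not that count rescaled.

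**Conclusion.** The point holds as a mismatch between the defined outcome and the estimator, of modest practical size. For any positive rho the two end urines carry more than a quarter of the weight. In a given data set the arm estimate will therefore generally differ from the mean count divided by 8, by an amount that depends on an estimated correlation. The weighting follows from the specified model alone. The 37-58% share needs the assumptions of step 3. The risk differences of 0.082 to 0.118 need, in addition, invented arm-specific end-visit rates, so they show sensitivity and do not forecast bias. Nothing here threatens type I error, and the sample size is hardly affected. The change is worth making because it aligns the analysis with the outcome at almost no cost.

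**What to change.** In Section 16.3.1 (text and code) and the synopsis, replace the AR(1) working correlation with TYPE=IND or TYPE=EXCH and keep the robust standard error. With eight records per participant, both give an arm estimate equal to the mean number of MA-negative urines divided by 8. Rerun Table 16.1 under the new specification and keep AR(1) as a named sensitivity analysis. Section 16.0 says a formal SAP is still to be written, so that is the natural place to carry the change.

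The cost is one word of code and a rerun of the power simulation. At N = 246, power changes by about +1 to -2 points, the loss arising if the true correlation is strongly AR(1). A side benefit is that record order no longer matters, whereas the printed AR(1) code names no visit variable.

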5.2 Secondary Objectives

Secondary objectives include evaluation of whether assignment to 12 weeks of outpatient BUP-Inj compared to 12 weeks of outpatient PBO-Inj improves:

1. Alternate measures of methamphetamine use:
 - a. Total number of MA negative UDS (Treatment Effectiveness Score, TES) through Weeks 1-12
 - b. Self-reported days of MA use (TLFB) through Weeks 1-12
2. Measures of opioid use:
 - a. Total number of opioid negative UDS (TES) through Weeks 1-12
 - b. Self-reported frequency of opioid use (TLFB) during Weeks 1-12
3. Measures of MA and opioid co-use:
 - a. Total number of MA and opioid negative same-day UDS (TES) through Weeks 1-12
 - b. Self-reported days of MA and opioid co-use (TLFB) during Weeks 1-12

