16.6 Exploratory Analysis

Exploratory analyses include:

1. *Measures of MA subjective effects*: both (a) MA withdrawal, as measured by scores on the Amphetamine Cessation Symptom Assessment during Weeks 1-12 and (b) self-reported MA craving as measured by the Visual Analog Craving Scales (VAS) during Weeks 1-12 will be analyzed by repeated-measures mixed-effects model. The model will have terms for time, treatment group, treatment group by time interaction, baseline measure of the outcome, and any covariates. Person effects will be random and all other effects fixed.

2. *Measures of opioid subjective effects*: All measures, (a) Observer rating of opioid withdrawal as measured by the Clinical Opiate Withdrawal Scale (COWS) on the day of randomization; each subsequent visit during induction in Week 1, if needed; prior to each injection in Weeks 1, 5, and 9; and at Week 12 ; (b) Self-reported rating of opioid withdrawal as measured by the Subjective Opiate Withdrawal Scale (SOWS) on the day of randomization; each subsequent visit during induction in Week 1, if needed; prior to each injection in Weeks 1, 5, and 9; and at Week 12; (c) Self-reported opioid craving, as measured by Visual Analog Craving Scales (VAS), during Weeks 1-12 will each be analyzed using repeated-measures mixed-effects models, with terms for time, treatment group, treatment group by time interaction, baseline measure of the outcome, and any covariates. Person effects will be random and all other effects fixed.
3. *Self-reported craving for MA and opioid co-use*: As measured by Visual Analog Craving Scales (VAS), during Weeks 1-12 will each be analyzed using repeated-measures mixed-effects models, with terms for time, treatment group, treatment group by time interaction, baseline measure of the outcome, and any covariates. Person effects will be random and all other effects fixed.

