4. *Measures of mood, pain and stress*: All measures, (a) Changes in self-reported depressive symptoms as measured by the IDS-SR during Weeks 1-12, (b) Changes in self-reported anxiety symptoms as measured by the GAD-7 during Weeks 1-12, (c) Changes in self-reported mood symptoms as measured by the CAST-IRR during Weeks 1-12, (d) Changes in self-reported anhedonia as measured by the DARS during Weeks 1, 5, 9, and 12, (e) Changes in self-reported pain as measured by the P-FIBS during Weeks 1-12, and (f) Changes in self-reported stress as measured by the PSS during the Weeks 1, 5, 9, and 12 will each be analyzed using repeated-measures mixed-effects models, with terms for time, treatment group, treatment group by time interaction, baseline measure of the outcome, and any covariates. Person effects will be random and all other effects fixed.
5. *Retention*, defined as the number of visits (0-24) present and providing urine drug samples during Weeks 1-12 will be analyzed similarly as described for the secondary outcome.
6. *Measures of Infectious disease control, incidence, and risk*:
 - a. Defined as the biomarkers measured at Week 12, remaining HIV-negative for those that started the trial HIV-Negative and remaining HCV-negative for those that started the trial HCV-Negative, will be analyzed using logistic regression with HIV status and HCV status as the outcomes, respectively, and treatment group and other covariates as predictors.
 - b. Self-Reported HIV transmission risk behaviors measured at Weeks 1, 6 and 12, defined as (a) Self-reported number of new sexual partners, (b) Self-reported number of sexual partners with condomless sex who are serodiscordant or unknown serostatus, (c) Self-reported number of sexual partners with condomless sex with partners who are serodiscordant or unknown serostatus with whom illicit substance were used (chemsex), (d) For men, self-reported

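### The methamphetamine Treatment Effectiveness Score is one total out of 24 per participant, so its planned interaction test does not exist; split by week, the rule gives two routes to success

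*Combined protocol and SAP*

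**What the plan says.** Section 5.2 gives the objective as "Total number of MA negative UDS (Treatment Effectiveness Score, TES) through Weeks 1-12". Section 7.2 defines the score with two possible samples per week and a range of 0 to 24.

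Section 16.3.2 item 1a anticipates a beta-binomial regression in which "the number of negative UDS is modeled as the number of 'successes' in 24 trials". The same paragraph continues: "The model will have terms for time, treatment group, treatment group by time interaction, baseline measure of the outcome, and any covariates". It closes with the decision rule: "The primary hypothesis will be tested by significance of the main effect or interaction effect". It defines no weekly or visit-level record, no coding of time and no within-participant correlation for this outcome. Item 1b, by contrast, lists a random participant effect.

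Nearly the same list of terms appears in Section 16.6 item 1 for weekly withdrawal and craving scores, where each outcome "will be analyzed by repeated-measures mixed-effects model. The model will have terms for time, treatment group, treatment group by time interaction".

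Section 16.4 sets a two-sided 5% level for the primary outcome only and makes no multiplicity adjustment across the secondary outcomes. Section 16.0 says that a formal SAP will follow.

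Two neighbouring texts are also unclear:

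- For the opioid and co-use outcomes (items 2 and 3), the closing sentence "will be analyzed using a hurdle model (ceiling effects are not expected) similarly as described for the secondary outcome 1b" can be read as covering the urine-based scores 2a and 3a as well as the self-reports 2b and 3b. Yet item 1a says: "Given the presence of ceiling and floor effects a more flexible model is needed than the hurdle model".
- Retention in Section 16.6 item 5, a count of visits, is described as "0-24) present and providing urine drug samples during Weeks 1-12 will be analyzed similarly as described for the secondary outcome". There are six secondary outcomes, and the text does not say which is meant.

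**The concern.** The outcome is a single number per participant, but the model and the test are written for repeated measurements. Read literally, the plan calls for a test that cannot be computed. If an analyst restructures the data by week so that it can be computed, the word *or* creates two ways to succeed on one outcome, with no order, alpha split or joint test.

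The interaction also answers a different question from Section 5.2. It asks whether the treatment difference changes over time, not whether the total is higher, and gains in some weeks can be offset by losses in others. Two analysts following item 1a could therefore run different tests and report different conclusions for the first-listed secondary outcome. Calling this the primary hypothesis adds to the confusion.

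**Working it through.** **The plan's own figure.** 2 samples per week × 12 weeks = 24, which agrees with Sections 7.2 and 16.3.2.

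**Reading 1: one total per participant, as written.** Let z be the treatment indicator. Time takes the same value c for everyone. The columns are then 1, z, c and c·z. The third is c times the first and the fourth is c times the second, so the rank is 2 of 4. Only the treatment coefficient can be tested, and there is no error inflation. This is algebra and needs no assumption.

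**Reading 2: twelve weekly counts of 0 to 2.** The rank is now 4 of 4 and both tests exist. Assume 5% for each, since the documents give no level for secondary outcomes.

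- Independent tests: 1 − 0.95² = 0.0975.
- Upper bound if each test is exactly 5%: 0.05 + 0.05 = 0.10.

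The rule was simulated under the null at N = 246, 1:1, with 24 binary screens per person. The screens came from a latent Gaussian model with a person share r of the variance and AR(1) correlation ρ. A baseline covariate correlated 0.3 with the person effect was in every model. Rates of 7% and 17% are those in Section 16.2, and 12% is their midpoint; r and ρ are assumptions. Because the plan does not specify a weekly model, a logistic model with participant-clustered, bias-corrected standard errors stood in for it. Each setting had 2,500 replicates (Monte Carlo SE 0.4 to 1.0 points across all runs). Each weekly test was calibrated to exactly 5%, so the either/or columns measure the rule alone.

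| Rate, r, ρ | Either/or, centred time | Either/or, time 1–12 | Joint 2-df test | Beta-binomial on the total, treatment only |
|---|---|---|---|---|
| 0.07, 0.5, 0.7 | 9.8% | 8.6% | 5.2% | 4.4% |
| 0.12, 0.5, 0.7 | 9.8% | 8.4% | 5.6% | 5.4% |
| 0.17, 0.5, 0.7 | 9.6% | 8.6% | 5.4% | 6.1% |
| 0.12, 0.3, 0.5 | 9.8% | 7.8% | 5.8% | 5.2% |
| 0.12, 0.6, 0.85 | 9.8% | 8.5% | 5.9% | 5.7% |

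Without calibration (|z| > 1.96), the either/or rule rejected in 8.8% to 11.2%. Separate GEE simulations with other correlation structures and time codings, also uncalibrated, gave 9.7% to 12.5%, with the single tests at 5.2% to 6.4%. The time coding matters because, once an interaction is in the model, the treatment main effect is the effect at time zero, wherever the coding puts it.

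**Equal totals.** Placebo is flat at 12%: 24 × 0.12 = 2.88 expected negatives. BUP-Inj moves linearly from 17% to 7%, or the reverse: 24 × (0.17 + 0.07)/2 = 2.88. At half the gradient: 24 × (0.145 + 0.095)/2 = 2.88. The share of trials declaring an effect (calibrated, centred time) was:

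| BUP-Inj path | r 0.5, ρ 0.7 | r 0.3, ρ 0.5 | r 0.6, ρ 0.85 |
|---|---|---|---|
| 17% to 7% | 72.2% | 82.1% | 61.1% |
| 7% to 17% | 70.9% | 81.9% | 61.5% |
| 14.5% to 9.5% | 26.4% | 31.7% | 22.4% |
| 9.5% to 14.5% | 26.4% | 31.7% | 23.2% |

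With time coded 1–12 the ranges were 62.8% to 82.7% at the full gradient and 23.7% to 31.9% at half. The beta-binomial test on the total declared an effect in 5.0% to 6.0% throughout. The treatment effect averaged over weeks did so in 4.1% to 6.1%.

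**The case against.** The strongest reply is that the error inflation belongs to a weekly model that the plan never describes. On the text as written, the aliased terms drop out and one valid treatment test remains. That stands, and it means that every inflation figure above is conditional on the weekly reading. The figures also move with the stand-in model, the time coding and the calibration.

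The equal-total example is constructed so that the totals cancel, and it borrows rates from the last four weeks of another trial's phase. That also stands. The arms do differ over time in that example, so 61% to 83% is not a false-positive rate for the interaction. It shows only that the rule can declare success on a total when the totals are equal.

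Two further replies do not remove the problem. Section 16.4 waives adjustment because the secondary outcomes are numerous, but it does not choose between two tests of the same outcome. Section 16.0 defers detail to a formal SAP, and item 1a calls the beta-binomial model only anticipated. However, the terms and the decision rule are stated firmly, so a SAP must either depart from them or inherit the fault.

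The side points are weaker. For items 2 and 3 the plan expects no ceiling effects, while item 1a asks for a more flexible model because it expects both ceiling and floor effects, so the texts do not directly contradict each other. Retention is scored 0 to 24, so item 1a is probably the model meant. Both need clarification and would not carry the concern alone.

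On missing samples, a count of negatives out of 24 already treats a missing sample as not negative. The baseline covariate, however, is undefined, because a score over 24 treatment-phase samples has no direct baseline equivalent. That gap needs filling.

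**Conclusion.** The concern holds. On the stated outcome the interaction test does not exist, and this rests on algebra alone. On the weekly alternative, either/or testing brings the error rate from 5% to nearly 10%: 9.75% under independence and 7.8% to 9.8% in calibrated simulation. That range assumes 5% per test, the correlation settings shown and a stand-in model. The interaction route also does not address the total named in Section 5.2. The effect is confined to a secondary outcome; the primary GEE analysis and N = 246 do not change. It should be corrected, because the rule is wrong as written and not merely lacking detail.

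**What to change.** In Section 16.3.2 item 1a, and in the formal SAP:

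- Fit the beta-binomial regression to each participant's total, with treatment and a named baseline MA measure. One candidate is days of use in the 30 days before consent, which item 1b already uses. Site, the randomization stratum in Section 16.1.3, may be added.
- Delete the time and treatment-by-time terms.
- Test the single treatment coefficient, two-sided at 5%, and show the weekly profile descriptively.
- Refer to the hypothesis for this secondary outcome, not to the primary hypothesis.

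If a time-resolved model is preferred, define the weekly or visit-level records (2 trials per week, not 24), the time coding and the handling of within-participant correlation. The last is essential: in a small simulation (120 runs per scenario), a weekly beta-binomial model with no participant effect gave a main-effect error of about 40% to 44%. Then name one deciding test. The treatment effect averaged over Weeks 1–12 matches Section 5.2. A joint 2-df test controls error at about 5% to 6% but does not test the total.

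Also state which model applies to items 2a and 3a, and which secondary outcome's model is meant for retention in Section 16.6 item 5.

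The cost is wording only, with no change to data collection or sample size. A pure change in effect over time would be described and not tested.
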